## 5 **SUB-STUDY 2: PERFORMANCE EVALUATION OF A TPHD LAMP ASSAY COMPARED TO QPCR FOR THE DIAGNOSIS OF YAWS-LIKE LESIONS**

### 5.1 **Objectives**

- 1) Evaluation of a TPHD LAMP assay performed in local hospitals compared to qPCR/PCR results obtained at the national reference laboratory in each country.
- 2) Testing the *Treponema pallidum* macrolide resistance (TPMR)-LAMP assay in a field setting
- 3) Development of an external quality assurance scheme for molecular diagnosis of yaws across endemic countries
- 4) Evaluating alternative methodologies for swab collection, DNA extraction and molecular testing

### 5.2 **Inclusion and exclusion criteria**

This study will consist exclusively of a subset of the individuals enrolled into sub-study 1 (case-finding). Participants will be consented for inclusion into sub-studies 2&3 at the same time as consent and enrolment into sub-study 1.

### 5.3 **Sample size**

We will collect samples for the TPHD LAMP evaluation from the 600 individuals with clinical and serological evidence of yaws, and an additional 10% of participants with clinical yaws but negative serology (sub-study 1). Based on the assumption that 35% of seropositive cases will also be positive by qPCR, this will result in approximately 210 qPCR positive *T. pallidum* cases and a similar number of *H. ducreyi* cases. This sample size will allow us to confirm that the TPHD-LAMP has both a sensitivity and specificity of at least 85% compared to the reference qPCR assays for both targets. This will also provide us with about 200 samples with unknown lesion aetiology to evaluate using next-generation sequencing as part of sub-Study 3.

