## 1.3 Study design:

This study will take place in three sub-Saharan African countries known to be endemic for yaws. We aim to screen approximately 60,000 participants, of all ages. Screened participants will undergo primary clinical examination for yaws-like lesions and will be classed as either suspected yaws or negative for active yaws. A proportion of the yaws free participants ( $\approx 10\%$ ) and all those with suspected yaws ( $\approx 6000$  people) will be invited to answer a questionnaire relating to household demographics and possible risk factors for yaws. If resources allow they will also be asked to provide dried blood spots for future serological analysis of yaws and other co-endemic neglected tropical diseases. Rapid point of care (POC) serological tests will then be used to confirm the clinical yaws diagnosis in the field, to allow for recruitment into the diagnostic evaluation study. Those with suspected yaws lesions will be tested with the SD Bioline syphilis test and those who test positive will be confirmed with the Chembio Dual Path Platform Syphilis Screen and Confirm POC test (herein DPP). As some cases of yaws occur in individuals who have not yet sero-converted, in order to improve the *Treponema pallidum pertenue* (TPE) prevalence estimate accuracy, we will collect lesion samples from all individuals with a dual seropositive DPP (treponemal and non-treponemal) and a subsample of the participants (1/10) negative for the SD Bioline or the DPP (either treponemal antibodies, non-treponemal antibodies or both). Two swabs, collected simultaneously from the same lesion, will be used for the diagnostic evaluation of the *T. pallidum* and *Haemophilus ducreyi* Loop-mediated isothermal amplification (TPHD LAMP) assay. Up to three further swabs may be collected from the same or additional lesions of the participant and from individuals with non-seroreactive tests but yaws-like lesions. We will also collect swabs of asymptomatic skin and of fomites of the house from some participants with and without yaws. These additional swabs will allow us to investigate other pathogenic causes of lesions using specific nucleic acid amplification tests and next generation sequencing. We will also be able to perform supplementary laboratory analysis on swab collection and DNA extraction methodologies, investigate the role fomites may have in the transmission of TPE and *H. ducreyi* and further understand the role of *H. ducreyi* as a cause of skin ulcers. No more than five lesion

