#### **1.5 Study participants and planned sample size:**

Patients of all ages in endemic districts will be recruited into the study. In total, we plan to perform an initial clinical screen on approximately 60,000 participants of whom we expect 6,000 will present with yaws-like lesions. Of these we expect around 600 individuals will have a dual positive DPP test and will therefore be eligible for the diagnostic evaluation.

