#### **3.1 Overall Study Outline and recruitment**

**Figure 1:** Flow chart of participant recruitment across all three-study countries. Initially we will screen 60,000 people of whom we expect 6000 will present with yaws-like lesions. These 6000 participants, along with 6000 without clinical evidence of yaws will be invited to take part in sub-study 1, the epidemiological analysis. All participants with clinically suspected yaws will be tested with a serology POC test, with positive results being confirmed by second POC test. Those with clinical and serological evidence of yaws will be invited to participate in sub-studies 2 and 3. Additionally, some participants from studies 1-3 along with healthcare workers and key stakeholders will be invited to enrol in study 4.

\* A DPP test is considered positive only if sero-reactive for both treponemal and non-treponemal antibodies.

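### Sections 1.5 and 3.1 tie entry to the LAMP evaluation to positive serology, while 5.3 also samples one in ten seronegatives; 5.3's counts cover only the seropositives, and 5.7 does not say in whom predictive values are estimated

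*Combined protocol and SAP*

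**What the plan says.** In this note, seropositive means a dual-positive DPP, and seronegative means a yaws-like lesion with a negative SD Bioline or DPP result.

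- **Section 5.3** collects evaluation samples from the 600 seropositives and from "an additional 10% of participants with clinical yaws but negative serology". It applies a 35% qPCR positivity rate to seropositive cases and expects about 210 T. pallidum positives and a similar number of H. ducreyi positives. It adds: "This will also provide us with about 200 samples with unknown lesion aetiology". For both targets it then states: "This sample size will allow us to confirm that the TPHD-LAMP has both a sensitivity and specificity of at least 85" per cent. It gives no assumed true accuracy, interval method or power.
- **Section 1.5** says: "Of these we expect around 600 individuals will have a dual positive DPP test and will therefore be eligible for the diagnostic evaluation".
- **Section 3.1** says: "Those with clinical and serological evidence of yaws will be invited to participate in sub-studies 2 and 3".
- **Section 1.3** points both ways. Serological tests are "used to confirm the clinical yaws diagnosis in the field, to allow for recruitment into the diagnostic evaluation study". The sampling sentence, whose stated purpose is prevalence, includes "prevalence estimate accuracy, we will collect lesion samples from all individuals with a dual seropositive DPP (treponemal and non-treponemal) and a subsample", and that subsample is one in ten of those with negative serology. The next sentence assigns the paired swabs to the evaluation without excluding anyone by serology.
- **Sections 4.5 and 5.4** send paired swabs to LAMP and PCR with no serological limit. Section 5.2 says only that sub-study 2 is a subset of sub-study 1.
- **Section 5.7** plans sensitivity and specificity for each target, and PPV and NPV against qPCR. It names no analysis set, no handling of serostatus and no confidence intervals.

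**The concern.** A person with a lesion but negative serology does not meet the basis for entry given in 1.5 and 3.1, yet may be sampled for the evaluation under 5.3. The sample size behind the 85% statement therefore has two readings, and 5.7 does not choose between them.

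More is at stake than precision. The two groups are sampled at very different rates, so the mix of patients in the data depends on which set is used. If accuracy is the same in both groups, sensitivity and specificity do not depend on that mix, but PPV and NPV do. Section 1.7 asks whether the test suits eradication programmes and surveillance, where those tested are people with suspected yaws, and most of them are expected to be seronegative. With the set left open, it could also be chosen after the results are known.

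**Working it through.** **Inputs from the documents.** 6,000 people with yaws-like lesions and 600 with serological confirmation (4.3); a one-in-ten sample of seronegatives (1.3, 4.5, 5.3); 35% qPCR positivity in seropositives, a similar number of H. ducreyi, and about 200 unknown (5.3).

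**Inputs that are assumptions.** True sensitivity and specificity of 95% each for the predictive values; qPCR positivity *q* in seronegatives from 0 to 35%, because the documents give no rate; no co-infection when counting unknown lesions.

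**1. Size of the two sets.** Seronegatives: 6,000 − 600 = 5,400. Sampled: 10% × 5,400 = 540. Total: 600 + 540 = 1,140. The 540 and 1,140 are derived; the protocol does not print them.

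**2. The plan's own counts.** 600 × 0.35 = 210, which reproduces the stated figure. 600 − 2 × 210 = 180 unknown, against about 200 stated. 210 + 210 + 200 = 620, which is close to 600 with rounding and far from 1,140. In the full set, with 35% H. ducreyi throughout, unknown lesions would number:
- *q* = 35%: 1,140 − 399 − 399 = 342
- *q* = 0: 1,140 − 210 − 399 = 531

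So the figure of about 200 fits only the 600. The 210 is correct for seropositives and is a floor for the full set.

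**3. Case mix.** Pooled: 600/1,140 = 53% seropositive. Among suspected cases: 600/6,000 = 10%.

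**4. T. pallidum PPV.** PPV = 0.95p / [0.95p + 0.05(1 − p)], where p is
- seropositives only: 210/600 = 35%, giving PPV 91.1%
- simple pool: (210 + 540*q*)/1,140
- weighted to all suspected cases: (210 + 5,400*q*)/6,000

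| *q* (assumed) | p pooled | PPV pooled | p weighted | PPV weighted |
|---|---|---|---|---|
| 0% | 18.4% | 81% | 3.5% | 41% |
| 5% | 20.8% | 83% | 8.0% | 62% |
| 10% | 23.2% | 85% | 12.5% | 73% |
| 35% | 35.0% | 91% | 35.0% | 91% |

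The three answers agree only if seronegatives are as often qPCR positive as seropositives.

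**5. The 85% statement.** It cannot be reproduced, because 5.3 gives no assumed accuracy or rule. For illustration, take an exact test against 85% at one-sided 0.025:
- Sensitivity in seropositives: 210 positives need 189 detected (90.0%). Power is 56% at a true 90%, 88% at 92% and 99.9% at 95%.
- Specificity in seropositives: 390 negatives need 346 correct. Power at a true 90% is 82%.
- Pooled, *q* from 0 to 35%: 210–399 positives and 930–741 negatives. Power at a true 90% is 56–83% for sensitivity and 98% or more for specificity.

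**The case against.** The strongest reply is that the protocol largely settles the set. Section 5.3 says outright that the seronegative samples are for the LAMP evaluation, and 4.5 and 5.4 route samples to both assays without regard to serology. Against these stand a synopsis line in 1.5 and a figure caption in 3.1. Neither uses an exclusive word, and the flow chart itself cannot be seen in the text reviewed. This has force: the larger set is the more natural reading. It does not remove the conflict, because 1.5 makes the positive DPP the stated reason for eligibility and 5.7 is silent. Nor does it help with predictive values, because the favoured reading is the one in which simple pooling misstates the case mix.

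Three stronger readings might be inferred and are not supported:

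- **That 1.3 also restricts the evaluation to 600 seropositives.** It gives no such figure, and its two-swab sentence follows mention of both groups. It is ambiguous, not contradictory.
- **That the 210 is an error.** Section 5.3 labels its rate as applying to seropositive cases.
- **That the PPV in suspected cases would be 62–73%.** That range needs 5–10% positivity in seronegatives, which no section supports; over 0–35% the range is 41–91%.

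It is also fair to say that the misfit in the unknown count bears mainly on sub-study 3, which has no formal sample size (6.3), and that 5.7 does not itself propose weighting.

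**Conclusion.** The point holds as an inconsistency in who enters the evaluation, together with an undefined population for PPV and NPV. Entry is described by seropositivity in 1.5 and 3.1 and more widely in 5.3, giving a base of about 600 or about 1,140. The printed counts describe only the 600.

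The main consequence is that a PPV or NPV from a simple pool would not apply to suspected cases. At 95% sensitivity and specificity, the T. pallidum PPV is 91% in seropositives, 81–91% pooled and 41–91% weighted. These ranges rest on the assumed accuracy and on *q* from 0 to 35%; they illustrate the issue and do not predict results.

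A reader might infer that the study is underpowered for the 85% claim. The documents do not show that: under the illustrative rule, sensitivity in the 600 has 99.9% power if the truth is 95% and 56% if it is 90%, and 5.3 does not say which is expected. The point should be settled before analysis, but it does not threaten the design.

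**What to change.** - **Sections 1.5, 3.1 and 1.3.** Bring 1.5 and 3.1 into line with 5.3 by stating that the one-in-ten sample of seronegatives also enters the evaluation. Clarify 1.3 in the same way.
- **Section 5.3.** Label the 210, the similar number of H. ducreyi and the roughly 180–200 unknown as seropositive counts. Give expected counts for the roughly 540 seronegatives with the rates assumed. State which set and which assumed true accuracy lie behind the 85% statement.
- **Section 5.7.** Report sensitivity, specificity, PPV and NPV with 95% confidence intervals by serostatus. For all suspected cases, give overall PPV and NPV with seronegatives weighted by the inverse of the sampling fraction (10 if it is exactly one in ten), with intervals that allow for the weights. This requires the one in ten to be chosen systematically or at random, which the protocol should state, since it does not do so now.
- **Choice of set.** Decide in advance whether the 85% conclusion rests on the seropositive stratum or on the pooled set. Either is defensible; the choice belongs to the investigators.

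The cost is wording and a short addition to the analysis, with no more participants or swabs. The downside is wide intervals for T. pallidum sensitivity in seronegatives (540 × 5% = 27 positives if 5% are qPCR positive, an assumption) and an overall PPV that is probably lower than in the 600.

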### 5.4 **Sample collection and Storage**

Samples will consist of lesion samples collected in sub-study 1 to be tested using both the TPHD LAMP assay (performed at the district/regional level) and qPCR/PCR (performed at each country's National Reference Laboratory). We will also test all *Treponema pallidum* positive samples for azithromycin resistance genes using the multiplex TPMR-LAMP assay and the gold standard resistance detection techniques performed at reference laboratories. Samples from the study will also be used to

undertake objectives 3-5; including development of an external quality assurance (EQA) scheme for yaws molecular diagnostics and evaluating optimal sample collection and processing approaches. These samples will also be used for sub-study 3.

## 5.5 Laboratory Procedures

For the diagnostic evaluation, samples will be transferred to both district and reference laboratories for testing under routine programmatic conditions. For reference PCR testing at the reference laboratory, DNA will be extracted from lesion samples. In the first instance, we will run PCRs targeting *T. pallidum* and *H. ducreyi*. A negative (no-template) control, positive controls for *T. pallidum* and *H. ducreyi* DNA and an extraction control will be included in each PCR run. In samples where *T. pallidum* is detected further PCRs targeting macrolide resistant point mutations A2058G and A2059G in the 23s RNA genes and to distinguish between different species of Treponemes will be run.

TPHD-LAMP and TPMR-LAMP will be performed at district laboratory level. DNA will be extracted using a commercial extraction kit deemed suitable for use in the field, the same kit will be used in all district laboratories. The TPHD-LAMP assay will be run in accordance with the manufacture-provided instructions. SOPs will be written by members of the LAMP4yaws consortium and provided to each of the laboratories. Incubation will be performed using the field compatible Tubescanner platform, which reads fluorescence signals for up to 4 different dyes. Final test results in terms of “positive”, “negative” or “invalid/retest” will be directly displayed on the screen using test methods developed by Mast (Mast Diagnostica GmbH, Germany).

All results, including raw and cleaned data from both reference and local laboratories will be electronically uploaded and deposited in the secure, encrypted central study database at LSHTM. Staff at district laboratories performing the TPHD-LAMP will be blinded to results from the national reference laboratories, and staff performing the PCR/qPCR at the national reference laboratories will be blinded to the TPHD LAMP results.

A subset of the additionally collected swabs taken from suspected yaws patients, the fomite swabs and some aliquots of DNA extracts will be shipped to the laboratories of the LAMP4YAWS consortium (see 1.11) for use in sub-study 3 and to run additional investigations into optimal sample collection and processing methods. These will include testing fomite swabs for the presence of *T. pallidum* or *H. ducreyi* and performing additional viability PCRs to determine if living bacteria can be detected on fomites in order to highlight if fomites are a key route of transmission. We will also use the TPHD-LAMP assay and reference qPCR to investigate if diagnostic accuracy can be enhanced by taking swabs

from multiple lesions of an infected patient. A selection of additional swabs and/or DNA extracts may be sent to various collaborating laboratories to enable the development of an external quality assurance (EQA) scheme.

## **5.6 Quality assurance for laboratory procedures at study sites**

The TPHD LAMP will be used at local hospital facilities close to the enrolled communities. Extensive training for this will take place prior to participant recruitment and we will conduct both internal and EQA activities throughout the study. Some aliquots of extracted DNA or additional lesion swabs will be exported to the European consortium laboratories and rechecked using both the TPHD-LAMP and gold standard (qPCR/PCR) for each pathogen. We will purposively select a higher proportion of samples for External Quality Assurance in the first six months of the laboratory testing to allow early detection of significant implementation problems. In case of significant differences between the reported results and the international reference laboratory results, an on-site evaluation will be initiated to identify the cause and solve the problem. All participating laboratories will work according to the GCLP guidelines, including internal quality assurance activities.

## **5.7 Data Analysis**

For the evaluation of the TPHD-LAMP assay compared to qPCR for the diagnosis of yaws, we will calculate the sensitivity and specificity of the *T. pallidum* and *H. ducreyi* targets individually compared to the respective reference qPCR assays. We may perform additional sub-analyses to assess if the performance of the TPHD-LAMP assay is related to bacterial load as measured by qPCR. The positive predictive value and negative predictive value will also be determined against the qPCR results.

## **6 SUB-STUDY 3: USE OF MOLECULAR TOOLS AND NEXT-GENERATION SEQUENCING TO UNDERSTAND THE AETIOLOGY OF YAWS-LIKE LESIONS, AND OPTIMISE SEQUENCING TOOLS FOR POINT OF CARE USE.**

### **6.1 Objectives**

- 1) Use nucleic acid amplification tests to investigate the presence of *Mycobacterium ulcerans*, *Leishmania* or *Corynebacterium diphtheriae* DNA in TPE and *H. ducreyi* negative swabs to determine if these pathogens are a significant cause of yaws-like lesions
- 2) Perform metataxonomic microbial analysis to determine other bacterial causes of yaws-like lesions when targeted pathogens are not detected through NAATs
- 3) Explore the evolution and transmission routes of resistant strains using whole genome phylogenetic analyses if macrolide resistant TPE are isolated
- 4) Optimise the Oxford Nanopore Minion sequencing for detection of TPE, *H. ducreyi*, and macrolide resistance strains of both pathogens, in the field
- 5) Perform investigations into the role of *H. ducreyi* as a significant cause of yaws-like lesions by measuring the presence of *H. ducreyi* on the skin of asymptomatic patients of all ages, using culture and molecular methods and genotyping any *H. ducreyi* detected from symptomatic or asymptomatic cases.
- 6) Detail the baseline resistance profiles of *H. ducreyi* using drug susceptibility assays

### **6.2 Inclusion and exclusion criteria**

As with sub-study 2, this study will consist exclusively of a subset of the individuals enrolled into sub-study 1 (Case-finding). Participants will be consented for inclusion into sub-studies 2&3 at the same time as consent and enrolment into sub-study 1.

### **6.3 Sample size**

There is no formal sample size for this sub-study.

### **6.4 Sample collection and storage**

As with sub-study 2, this study will utilise the samples collected from participants in sub-study 1. These will be stored in country and a sub-set will be sent to the laboratories of the consortium in Europe.

### **6.5 Laboratory Procedures**

Tests will be performed in the laboratories having the assays, platform and equipment in place or under development for the purpose. For all NAATs and sequencing techniques, DNA will be extracted from lesion swabs using a suitable commercial kit specially designed or adapted for swab

extraction. Targeted tests for *Mycobacterium ulcerans*, Leishmania or *Corynebacterium diphtheriae* will be performed using qPCR. To detect *H. ducreyi* from fomite swabs or asymptomatic skin, swabs will be inoculated on enriched culture media before being tested using qPCR. Genotyping using whole genome sequencing (WGS) or multilocus sequence typing (MLST) will be performed on the *H. ducreyi* cultures obtained. Genotyping directly from swab DNA extracts, without the need for enrichment culturing, will also be tested. These activities will be led by the Centre Pasteur du Cameroun.

For Illumina and Minion WGS sequencing, qPCR will be used to select samples with a higher bacterial presence. DNA fragmentation and library preparation will be performed using a suitable commercial kit for the sequencing platform. We will then sequence using manufacture guidelines or methodology optimised within house. A range of open source software will be used to highlight low quality reads, clean data and complete assembly of genomes using established reference strains.

For metataxonomic sequencing, the variable region 4 (V4) of the 16S ribosomal RNA gene will be targeted. A blank control (microbial DNA-free water) and a mock control sample will be included into the analysis. Amplicon triplets will be pooled and purified using AMPure XP beads (Beckman Coulter). Sequencing will be done using Illumina technology (MiSeq 2x250 bp paired-end sequencing), following published guidelines .

## 6.6 Data Analysis

Whole genome sequencing: We will compare any sequences *T. pallidum* or *H. ducreyi* to reference strains to highlight single nucleotide polymorphisms, or any other structural differences. We will create phylogenetic trees to compare relatedness. We will use the same technology to explore how antibiotic resistance may have spread around the participating communities and if it is caused by the two common resistance mutations or novel mutations. Data management will fall under the responsibility of the lead investigator of the laboratory conducting each test and will be shared with other members of the consortium if requested.

